9.14 Abnormal Liver Function Monitoring and Drug-Induced Liver Injury Monitoring

Subjects will be monitored for liver function tests throughout the study, including transaminases, total bilirubin, complete blood count, serum alkaline phosphatase, prothrombin time/INR, and creatine kinase. If a subject develops a liver function test abnormality, promptly investigate with repeat biochemical and physical evaluation and notify the CRA immediately (refer to Section 4.3 for detailed procedures).

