9.14.1 Abnormal Liver Function

Weekly monitoring of liver function tests is required under the following conditions:

- Subject with a non-elevated liver function test at baseline is found to have any abnormal liver function test elevation that does not meet the stopping rules or discontinuation criteria (Section 9.4) or withdrawal criteria (Section 4.4); or
- Subject who is enrolled with a baseline liver function test that is $\leq 1.5 \times$ ULN and subsequently has an elevation $2 \times$ that of the baseline value.

Weekly monitoring shall continue for these subjects until their liver function tests return to below baseline value(s).

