9.14.2 Suspected Drug-Induced Liver Injury

Subjects will be monitored for DILI from randomization to 21 days following the last administration of study drug (refer to Appendix D for detailed procedures). Subjects must be immediately withdrawn from the study and follow the evaluation for suspected DILI in Appendix D, if they meet any of the following criteria:

- ALT or AST $>8 \times$ ULN;
- ALT or AST $>5 \times$ ULN for more than 2 weeks;
- ALT or AST $>3 \times$ ULN **AND** total bilirubin $>2 \times$ ULN or INR $>1.5 \times$ ULN; or
- ALT or AST $>3 \times$ ULN with the appearance of fatigue, nausea, vomiting, right upper quadrant pain or tenderness, fever, rash, and/or eosinophilia ($>5\%$).

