2.0 INTRODUCTION

Hepatotoxicity is injury or damage to the liver that may be associated with impaired liver function (Navarro and Senior 2006). Drug-induced hepatotoxicity is one of the most common causes of termination of drug development, a major reason for refusal of market authorization and for restricted use, and the single most important cause of the withdrawal of market authorization for products (Björnsson 2006). Thus, drug-induced hepatotoxicity is a major concern during the discovery, development to post-authorization phases of the product life cycle (excerpted from Draft Guidance Document, Hepatotoxicity of Health Products, Ministry of Public Health, Canada, December 2010).

As stated in the United States Food and Drug Administration (FDA) "Guidance for Industry - Drug-Induced Liver Injury: Premarketing Clinical Evaluation"; hepatocellular injury (usually detected by serum aminotransferase elevations [AT]) can be caused by drugs that rarely, if ever, cause severe DILI (e.g., aspirin, tacrine, statins, and heparin), as well as by drugs that do cause such injury. The frequency of serum AT elevations also is not a good indicator of a potential for severe DILI because drugs such as tacrine (not a cause of severe DILI) can cause AT elevations in as many as 50 percent of patients. Very high levels of observed ATs may be a somewhat better indicator of potential for severe DILI, but the most specific indicator is evidence of altered liver function accompanying or promptly following evidence of hepatocellular injury.

The single clearest (most specific) predictor found to date of a drug's potential for severe hepatotoxicity, is the occurrence of hepatocellular injury (AT elevation) accompanied by increased serum total bilirubin (TBL) not explained by any other cause, such as viral hepatitis or exposure to other hepatotoxins, and without evidence of cholestasis, together with an increased incidence of AT elevations in the overall trial population compared to control. Increased plasma prothrombin time, or its international normalized ratio (INR), a consequence of reduced hepatic production of Vitamin K-dependent clotting factors, is another potentially useful measure of liver function that might suggest the potential for severe liver injury.

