3.0 CLOSE OBSERVATION RECOMMENDATIONS

The following steps should be taken when a subject is observed to meet one of the following conditions:

- Elevation in ALT and/or AST $>3 \times$ ULN
- Suspected DILI, defined as:
 - ALT or AST $>8 \times$ ULN;
 - ALT or AST $>5 \times$ ULN for more than 2 weeks;
 - ALT or AST $>3 \times$ ULN **AND** total bilirubin $>2 \times$ ULN; or International Normalized Ration (INR) $>1.5 \times$ ULN
 - ALT or AST $>3 \times$ ULN with the appearance of fatigue, nausea, vomiting, right upper quadrant pain or tenderness, fever, rash, and/or eosinophilia ($>5\%$).

Initiate **close observation**, defined below, and continue performing **follow-up to resolution**.

Close observation is defined as follows:

- Repeat liver enzyme and serum bilirubin tests two (2) or three (3) times weekly. Frequency of retesting can decrease to once a week or less if abnormalities stabilize or study drug has been discontinued and the subject is asymptomatic.
- Obtain a more detailed history of symptoms and prior or concurrent diseases. (See Section 5).

Site Guidance Document for Assessment of Potential DILI

- Obtain a history of concomitant medication use (including prescription and nonprescription medications, herbal and other dietary supplements), alcohol use, recreational drug use and special diets. (See Section 4 for details.)
- Obtain a history of exposure to chemical agents or other environmental toxins.
- Obtain additional history and complete Stage 1 work-up to attempt to rule out other potential causes of the transaminase elevation, including but not limited to the following: acute viral hepatitis types A, B, C, D, and E; autoimmune or alcoholic hepatitis; non-alcoholic steatohepatitis (NASH); hypoxic/ischemic hepatopathy; and biliary tract disease. (See Section 5.5 for details.)
- Consider gastroenterology or hepatology consultation.

In general, treatment with study therapy should be stopped if the laboratory criteria for potential DILI are met. Please refer to the specific discontinuation criteria in the protocol as appropriate.

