7.5.2.1 Liver Enzymes and Total Bilirubin

The liver safety assessments will be summarized by the following categories below based on the measurements from Alkaline Phosphatase (ALP), Alanine Transaminase (ALT), total bilirubin, Aspartate Transaminase (AST), and their combinations are defined. These parameters will be measured from a central lab. The subject's highest value during the treatment period will be used.

Parameter	Potentially Clinically Significant Criteria
ALT	>3 x ULN
	>5 x ULN
	>8 x ULN
	>10 x ULN
	>20 x ULN
AST	>3 x ULN
	>5 x ULN
	>8 x ULN
	>10 x ULN
	>20 x ULN
ALT or AST	>3 x ULN
	>5 x ULN
	>8 x ULN
	>10 x ULN
	>20 x ULN
ALP	>1.5 x ULN
Total bilirubin	>1.5 x ULN
	>2 x ULN
ALT or AST and total bilirubin (*)	ALT or AST >3 x ULN and total bilirubin >2 x ULN
ALT or AST, ALP, and total bilirubin (*)	ALT or AST >3 x ULN, ALP <2 x ULN, and total bilirubin >2 x ULN

(*) Combination of values measured within the same day or up to one day apart.

The denominator for each criterion will be the number of subjects who have at least one value during the treatment period. The number and percentage of subjects meeting the criteria during the treatment and follow-up periods will be summarized by treatment group.

A detailed listing will be provided for subjects with suspected drug-induced liver injury (DILI).

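### The one-day pairing rule in SAP 7.5.2.1 can leave a bilirubin rise that follows a transaminase rise out of the by-arm combined count, once ALT and AST have fallen to 3 x ULN or below

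*SAP*

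**What the plan says.** SAP 7.5.2.1 has two combined rows. One is "ALT or AST >3 x ULN and total bilirubin >2 x ULN". The other adds ALP <2 x ULN. Both carry the footnote "Combination of values measured within the same day or up to one day apart". The lead-in to the table says "The subject's highest value during the treatment period will be used", but not how that works with the pairing rule. The section then reports subjects meeting the criteria in the treatment and follow-up periods and promises a listing of suspected DILI cases, without defining them. SAP 7.5 restricts safety data to one day after the last dose, apart from adverse events and follow-up visit data.

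Protocol 4.4, 9.4 and 9.14.2, and Appendix D section 3.0, use the same ALT/AST and bilirubin thresholds (with INR >1.5 x ULN as an alternative to bilirubin) and give no time window between the values. Appendix D section 2.0 names as the most specific indicator "evidence of altered liver function accompanying or promptly following evidence of hepatocellular injury".

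On test frequency:
- Protocol 9.14.1: "Weekly monitoring of liver function tests is required under the following conditions".
- Appendix D section 3.0: "Repeat liver enzyme and serum bilirubin tests two (2) or three (3) times weekly".
- Protocol 9.14, for a first abnormality: "promptly investigate with repeat biochemical and physical evaluation and notify the CRA immediately".
- SAP 3.2: site visits every 2 weeks during treatment.

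**The concern.** The table captures liver dysfunction that accompanies the injury but has no row for dysfunction that follows it, although Appendix D names both. If bilirubin crosses its threshold only after the transaminases have dropped back, the subject met both thresholds within days, yet the joint count omits her.

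A combined case is the liver finding to which a reader of a 352-subject dose-ranging trial would give most weight. ALT or AST >3 x ULN is an adverse event of special interest, and the combination is among the withdrawal and study-stopping criteria. With 44 women planned per arm, a zero in the combined row could be read as no subject having reached both thresholds. The table would not support that reading.

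**Working it through.** The plan states no figure to reproduce. The check compares the pairing window with the test intervals, then asks when a delayed bilirubin rise is lost.

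**Step 1: window against planned gaps**

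| Source | Frequency | Gap in days |
|---|---|---|
| SAP 7.5.2.1 | pairing window | 0 to 1 |
| Protocol, Appendix D 3.0 | 3 times weekly | 7/3 = 2.3 on average |
| Protocol, Appendix D 3.0 | 2 times weekly | 7/2 = 3.5 on average |
| Protocol 9.14.1 | weekly | 7 |
| SAP 3.2, visit window ±3 days | every 2 weeks | 14 (8 to 20) |
| Protocol 9.14 | prompt first repeat | not stated |

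Every planned gap with a stated frequency averages more than one day. Unless a prompt first repeat or an unscheduled test falls within a day, an ALT value cannot be paired with the bilirubin from the next test.

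**Step 2: when the case is lost**

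Close observation repeats enzymes and bilirubin together, so a later bilirubin >2 x ULN comes with its own ALT/AST. The subject is counted if either is still >3 x ULN in that draw or within a day of it, and lost if both are ≤3 x ULN. An example is ALT 3.5 x ULN at one test, then ALT 2.8 with bilirubin 2.2 x ULN at the next planned test (AST not above 3 x ULN). Neither draw crosses both thresholds and they are more than a day apart, so she is in neither combined row.

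**Step 3: illustration with assumed kinetics**

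Suppose ALT falls exponentially from a peak of M x ULN with half-life h days. Both are assumptions. Days above 3 x ULN after the peak = h × log2(M/3).

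| M | h | Days above 3 x ULN | Still >3 x ULN at gap of |
|---|---|---|---|
| 3.5 | 1 to 7 | 0.2 to 1.6 | none from 2 to 14 days |
| 5 | 4 | 2.9 | 2 days; not 3 or more |
| 8 | 4 | 5.7 | 2 to 4 days; not 7 or 14 |
| 10 | 7 | 12.2 | 2 to 7 days; not 14 |

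**Step 4: can a miss rate be given?**

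Simulation: peak uniform on 4 to 12 x ULN, bilirubin >2 x ULN for 7 days, random test timing. The table shows the share of cases with both elevations observed but never in the same draw.

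| Assumed ALT half-life | Bilirubin lag after ALT peak | Tests every 3.5 days | Weekly tests |
|---|---|---|---|
| 2 to 4 days | 0 days | 0% | 0% |
| 2 to 4 days | 1 day | 16% | 25% |
| 2 to 4 days | 3 days | 60% | 68% |
| 2 to 4 days | 5 days | 91% | 93% |
| 4 to 8 days | 3 days | 16% | 27% |
| 4 to 8 days | 5 days | 35% | 49% |

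The answer runs from 0% to over 90% according to inputs the documents do not contain. The failure mode is established; its frequency is not.

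**Step 5: the data cut-off**

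SAP 7.5 ends most safety data one day after the last dose. SAP 7.5.2.1 takes the highest value from the treatment period but counts criteria met in the treatment and follow-up periods. Protocol 9.14.2 monitors for DILI until 21 days after the last dose. Retests after stopping, where a following bilirubin rise could appear, may therefore be excluded unless they are follow-up visit data.

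**The case against.** The other side has a good deal to say.

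- **The rise is usually counted.** A reader might infer that any bilirubin rise first seen at the next retest is missed. That does not follow: it is counted whenever ALT or AST remains >3 x ULN in that draw. This stands and limits the point.
- **The subject is visible elsewhere.** She is in the ALT/AST >3 x ULN row and the bilirubin >2 x ULN row, both by arm. SAP 7.5.1 also gives ALT/AST elevation a special-interest summary, listing and graph. This stands, so the DILI listing is not her only trace. But separate rows cannot show that one woman met both thresholds, and the listing has no stated criteria and gives no count by arm.
- **Concurrency is a reasonable definition.** Appendix D section 2.0 gives laboratory criteria with the ALP value taken at the same time, and protocol silence on timing does not prescribe sequential pairing. This stands: the SAP does not contradict the protocol. It implements one of the two patterns that Appendix D describes, which is why the one-day rows should stay.
- **The example is not a diagnosed severe case.** Appendix D also asks that other causes and cholestasis be ruled out. Agreed; the example shows only what the table counts.
- **Peaks.** Read literally, the highest-value sentence would require the ALT and bilirubin peaks to fall within a day of each other. That reading is strained, since the footnote speaks of combinations of measured values. It calls for clarification and is not a demonstrated defect.

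**Conclusion.** The point holds in a limited form. The one-day rule can omit from the by-arm combined count a subject whose bilirubin exceeds 2 x ULN only after ALT and AST have fallen to ≤3 x ULN. It loses nothing when both rise together or when the transaminases are still >3 x ULN at the later draw. The effect is on one tabulated count: one omitted case changes an arm's entry from 1/44 to 0/44 (planned arm size). No percentage should be attached, because the result depends on assumed half-life, peak and lag. A reader might also infer that the plan would conceal such a case or weaken subject protection. The documents do not support that: the single-analyte rows and special-interest outputs remain, and the withdrawal and stopping criteria do not use the SAP footnote. This is an inexpensive improvement to the safety tables and does not affect the efficacy conclusions.

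**What to change.** In SAP 7.5.2.1:

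1. Keep the two one-day rows unchanged.
2. Add two supplementary rows for ALT or AST >3 x ULN with total bilirubin >2 x ULN on the same day or at a later test within a pre-specified longer window, with and without ALP <2 x ULN. Fourteen days, the scheduled test interval, is one defensible choice; any time on study is another. State which values the ALP condition applies to.
3. State that all combined rows use every eligible pair of values, not each subject's peaks.
4. State that retests after the last dose count for these rows, and reconcile the SAP 7.5 cut-off with the treatment and follow-up periods named in 7.5.2.1.
5. Define the suspected-DILI listing by the protocol 9.14.2 criteria.

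The cost is SAP wording and two table rows, before unblinding. A few unrelated bilirubin rises may be flagged and need narrative review. No threshold, test schedule or clinical rule changes.

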7.5.3 Vital Signs

The baseline visit is the last measurement taken prior to initial study drug administration.

Vital signs (systolic blood pressure, diastolic blood pressure, pulse rate, and temperature) will be summarized using mean, standard deviation, minimum, median, maximum, 10%, 90%, and lower and upper quartiles by treatment group and visit. Additionally, a within-subject

change will be calculated per visit as the post-baseline measurement minus the baseline measurement and summarized by treatment group and visit.

7.5.4 Electrocardiograms (ECGs)

The baseline visit is the last measurement taken prior to initial study drug administration.

ECG variables will be summarized using (n), mean, standard deviation, minimum, median, maximum, 10%, 90%, and lower and upper quartiles for each treatment group at each treatment visit, including changes from baseline.

Number and percent of subjects with normal, not clinically significant abnormal, and clinically significant abnormal results as assessed by investigator for the 12 lead ECG will be tabulated by treatment group at each treatment visit. Local readings and central readings will be summarized separately.

The QT intervals (QT, QTcB, and QTcF) will be summarized using frequency tables for each treatment visit (excluding Visits 2A, 3A, and 4A) and time point for values of clinical importance using the range criteria below.

QT Interval Criteria (msec)	Description
≤450	Normal
>450	Borderline
>480	Prolonged
>500	Clinically significant

The QT intervals will also be summarized by the frequencies of subjects with a change from baseline of clinical importance using the criteria identified below. These summaries will be provided for each treatment visit and time point.

Parameter	Change from Baseline Criteria
QT Interval (msec)	<0
	≥0
	>30
	>60

Number and percent of subjects whose 12 lead ECG reading changed from normal at baseline to abnormal will be tabulated by treatment group for each visit.

7.5.5 Pregnancies

A detailed listing of all pregnancies will be provided.

7.5.6 Other Safety-Related Observations

Endometrial health assessment results from transvaginal ultrasound and endometrial biopsy will be listed.

Mammogram results, plasma bone density marker concentration, and C-SSRS results will be listed.

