Clinically significant abnormal laboratory or other examination (eg, ECG) findings that are detected during the study or are present at the screening visit and significantly worsen during the study should be reported as adverse events. The Investigator will exercise his or her medical and scientific judgment in deciding whether an abnormal laboratory finding or other abnormal assessment is clinically significant. Clinically significant abnormal laboratory values occurring during the clinical study will be followed until repeat tests return to normal, stabilize, or are no longer clinically significant. Any abnormal test that is determined to be an error does not require reporting as an adverse event.

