9.16 Columbia Suicide Severity Rating Scale

The C-SSRS will be collected at Day 1 (Visit 2), Week 12 (Visit 5)/ET, and the follow-up visit (Week 15 [Visit 6]).

The C-SSRS will be used to assess all suicidal events and provide a summary of suicidal ideation and behavior. It assesses the lethality of attempts and other features of ideation (frequency, duration, controllability, reasons for ideation, and deterrents), all of which are significantly predictive of completed suicide. The questionnaire will be paper-based and administered at the study site prior to any invasive procedures.

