9.18 Endometrial Biopsy

Subjects will undergo endometrial biopsy (Pipelle) at the following timepoints:

- At screening, if endometrial thickness is ≥ 4 mm determined by transvaginal ultrasound;
- At Week 12 (end-of-treatment) – all subjects;
- At the ET Visit for subjects who are withdrawn from the study prior to completion, if exposure to study drug is ≥ 10 weeks; and
- In all cases of uterine bleeding.

Although the transvaginal ultrasounds (see Section 9.17) will be read centrally, a local transvaginal ultrasound reading at screening should guide the decision to perform endometrial biopsy or not. In the event the local reader measures an endometrial thickness ≥ 4 mm, a single biopsy will be taken from the thickest part of the endometrium. Refer to the FDA draft guidance.²³ In the event an inadequate specimen is obtained at screening, 1 repeat biopsy may be performed if technically possible. If the biopsy is abnormal at Week 12 (end-of-treatment), subjects will have a repeat biopsy 4 weeks later, if clinically indicated. All biopsies will be read by centrally by a blinded pathologist.

In the event that subject's biopsy indicates hyperplasia, biopsies will be assessed by 2 additional blinded pathologists. The participating study pathologists will be from different institutions with independent fiduciary and organizational reporting and will be blinded to each other's assessments. Concurrence of 2 of the 3 pathologists will be accepted as the final diagnosis. If the 3 pathologists do not agree, the most severe pathologic diagnosis would be used as the final diagnosis.

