10.2.2 Analysis of Safety

Safety will be assessed by examining the incidence of adverse events, physical examinations findings, C-SSRS, vital signs, ECGs, clinical laboratory tests, and bone density marker concentrations over time using the Safety Analysis Set.

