6.2 Safety Variables

Safety variables will include the following:

- Incidence and severity of treatment-emergent adverse events (TEAEs);
- Endometrial health assessment (transvaginal ultrasound ± endometrial biopsy);
- Vital signs (sitting systolic and diastolic blood pressure and pulse rate);
- Laboratory tests (hematology, biochemistry, urinalysis, and coagulation);
- 12-lead electrocardiogram (ECG) parameters;
- Plasma bone density marker concentrations;

- Physical examinations; and
- Columbia Suicide Severity Rating Scale (C-SSRS).

A TEAE is defined as an adverse event observed after starting administration of study drug through 7 days after the last dose of study drug. If the adverse event occurs on the day of the first dose and the onset time is on or after the time of the first dose of study drug or the onset time is missing, then the adverse event will be considered treatment emergent. If the adverse event occurs on the day of first dose and the onset time is before the time of the first dose of study drug, then the adverse event will not be considered treatment emergent. If a subject experiences an event both during the pre-investigational period that continues into the investigational period, the event will be considered as TEAE only if it has worsened in severity (i.e. it is reported with a new start date).

A drug-related TEAE is defined as any TEAE related to study treatment as assessed by the investigator or with missing assessment of the causal relationship.

Other safety endpoints will be considered treatment emergent if observed after starting administration of study drug through 1 day after the last dose of study drug.

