7.5 Analysis of Safety

All analyses of safety will be presented by treatment group for SAF, unless specified otherwise. For analyses by visit, the visit windows from Section 7.10.6 will be applied. Except for adverse events and follow-up visit data, only data up to one day after the last dose date will be considered for the analyses.

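### The SAP specifies listings and no by-arm summary for transvaginal ultrasound, endometrial biopsy and C-SSRS results, although it names all of them as safety variables

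*SAP*

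**What the plan says.** SAP 6.2 lists the safety variables. They include an entry beginning "Endometrial health assessment (transvaginal ultrasound ± endometrial biopsy", plus bone markers and the C-SSRS.

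SAP 7.5.6 is the only section that says how the endometrial and C-SSRS results will be presented. It has two sentences: "Endometrial health assessment results from transvaginal ultrasound and endometrial biopsy will be listed", and "Mammogram results, plasma bone density marker concentration, and C-SSRS results will be listed".

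SAP 7.5 sets the general default: "All analyses of safety will be presented by treatment group for SAF, unless specified otherwise".

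The protocol collects these data systematically. Protocol 9.18 schedules a biopsy "At Week 12 (end-of-treatment) – all subjects"; under inclusion criterion 8, women with a partial or full hysterectomy are exempt. Biopsies are read centrally and blinded, and a hyperplasia reading goes to two further pathologists for one final diagnosis. Protocol 9.17 has every ultrasound read locally and then centrally. The C-SSRS is completed at Day 1, Week 12/ET and follow-up (Protocol 9.16).

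On analysis, Protocol 10 says that everything collected will be reported through summary tables and figures as well as subject listings. Protocol 10.2.2 begins: "Safety will be assessed by examining the incidence of adverse events, physical examinations findings, C-SSRS". It continues with other variables and ends by saying they are examined over time in the Safety Analysis Set.

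**The concern.** This is a dose-ranging trial meant to select a Phase 3 dose. A safety variable measured in nearly every subject should therefore be readable by arm. A line listing of up to 352 women in 8 arms shows each individual case. It does not give the number of women assessed in each arm, the distribution of endometrial thickness or its change, or a rate with an interval.

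The cost falls most heavily on endometrial thickness. It is continuous, and a modest dose-related shift cannot be seen by reading rows. For hyperplasia and suicidal ideation the individual cases would be visible, but the denominator that turns a count, including a count of zero, into a statement about risk would be missing.

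**Working it through.** The plan gives no figure on this point, so there is none to reproduce. The check is mainly of the text, with one calculation for scale.

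**1. Is a by-arm summary planned elsewhere?**

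| Safety variable | Presentation | Where |
|---|---|---|
| Laboratory tests | By arm and visit, change, shift tables | SAP 7.5.2 |
| Liver tests | By-arm counts by threshold | SAP 7.5.2.1 |
| Vital signs | By arm and visit, change | SAP 7.5.3 |
| ECG | By arm and visit, local and central readings separate | SAP 7.5.4 |
| Bone markers | By arm and visit, change; also listed | SAP 7.4.2; 7.5.6 |
| Ultrasound, biopsy | Listed | SAP 7.5.6 |
| C-SSRS | Listed | SAP 7.5.6 |

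Where the SAP intends a table it says so. For the last two rows it does not. The by-arm default in SAP 7.5 governs how an analysis is laid out; it does not create one where a listing is specified.

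**2. Is the choice recorded as a change?** SAP 8 lists two changes from protocol: weight and waist circumference, and the daytime and night-time endpoints. Neither concerns these variables.

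**3. Do the adverse-event tables fill the gap?** Protocol 9.1 covers "Clinically significant abnormal laboratory or other examination (eg, ECG) findings that are detected during the study" and requires them to be reported as adverse events. SAP 7.5.1 tabulates TEAEs by arm, and the events of special interest, which include uterine bleeding, get a summary table. Three limits remain:

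- *Judgement.* Under Protocol 9.1 the investigator decides what is clinically significant. A shift in thickness within an unremarkable range, or low-grade ideation on the C-SSRS, need not be reported.
- *Window.* SAP 6.2 closes the TEAE window 7 days after the last dose. The follow-up C-SSRS comes about 3 weeks after the last dose, and a repeat biopsy 4 weeks after Week 12. An event first dated then falls outside.
- *Denominator.* TEAE percentages are presented for the SAF. That set includes women with no uterus and women who stopped before 10 weeks, who have no routine early-termination biopsy.

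**4. What could a table show?** With 0 events in n women, the exact upper limit is 1 − 0.05^(1/n) for a one-sided 95% bound and 1 − 0.025^(1/n) for a two-sided 95% interval.

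- n = 44 (planned arm): 1 − 0.05^(1/44) = 6.6%; 1 − 0.025^(1/44) = 8.0%. The rule of three gives 3/44 = 6.8%.
- n = 40 (the SAP's number per arm before its allowance for about 10% discontinuation): 1 − 0.05^(1/40) = 7.2%; 1 − 0.025^(1/40) = 8.8%.
- n = 7 × 44 = 308 (all active arms): 1 − 0.05^(1/308) = 0.97%; 1 − 0.025^(1/308) = 1.2%.

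These bounds assume that every woman counted was assessed. The documents do not say how many will have had a hysterectomy, so the biopsy limits will be wider by an amount that cannot be stated.

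**The case against.** The best defence is that SAP 7.5.6 does not say these results will be listed and nothing more. Elsewhere the SAP both summarises and lists: protocol deviations, events of special interest and, taking SAP 7.4.2 and 7.5.6 together, bone markers. Protocol 10 promises tables for all data, and SAP 7.1 leaves table formats to TLF specifications that are not available here. Tables may therefore be produced. That stands as a possibility. But for each of those examples the SAP names the summary, and for these outcomes it names none.

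Four stronger readings are tempting, and the documents do not support them.

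- *No by-arm information at all will exist on these risks, so the biopsies add almost nothing.* This is too strong. Clinically significant findings can reach the TEAE tables, uterine bleeding is tabulated, and a listing shows every hyperplasia case after central reading.
- *The plan contradicts itself on bone markers.* SAP 7.4.2 summarises them by arm, and listing them as well is compatible with that. The wording needs a cross-reference; it is not a firm conflict.
- *All of these outcomes are obtained by invasive procedures.* The C-SSRS is not: "The questionnaire will be paper-based and administered at the study site prior to any invasive procedures".
- *Listing the endometrial results departs from Protocol 10.2.2.* That section does not name ultrasound or biopsy. It supports the argument for the C-SSRS only, and only if the closing reference to change over time covers the whole list.

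It is also fair to say that no primary conclusion or multiplicity-controlled test is touched.

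**Conclusion.** The point holds as a gap in the safety reporting. For ultrasound, biopsy and C-SSRS results the SAP specifies listings and no by-arm descriptive summary. This sits poorly with SAP 6.2, with the general promise in Protocol 10 and, for the C-SSRS, with Protocol 10.2.2. The adverse-event tables are a partial and indirect substitute.

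The gain from correcting it is real but modest. Per-arm tables would be descriptive: even with no hyperplasia in a full arm of 44, a true rate of several percent could not be excluded. The pooled active arms would say more, with an upper limit near 1% if all 308 women were evaluable. The conclusion rests on the SAP text alone and assumes that the unseen TLF specifications do not already add these tables. If they do, the SAP needs only a sentence saying so.

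**What to change.** Add to SAP 7.5.6, by treatment group and for all active arms combined:

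1. **Endometrial thickness:** number scanned, and descriptive statistics at baseline (the screening scan), Week 12/ET and change. State that the central reading is used.
2. **Biopsy:** counts of each final diagnosis, after adjudication where it applies, with the number of women biopsied as denominator and exact 95% intervals. Present these as post-baseline findings, not change, because screening biopsy is not done in every woman.
3. **C-SSRS:** counts of ideation and behaviour categories at Day 1, Week 12/ET and follow-up, with the number assessed at each visit.

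State which post-treatment results are included. SAP 7.5 otherwise keeps only data up to one day after the last dose, apart from adverse events and follow-up-visit data, and early-termination or repeat biopsies may come later than that.

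Keep the listings. For bone markers, refer from SAP 7.5.6 to the by-arm summary in SAP 7.4.2. Label the tables descriptive, with no tests.

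The cost is a few extra tables from data already collected. There is no new procedure and no effect on sample size or the efficacy analysis. The change should be made before database hard lock.
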